# **Document History**

Revision date	Author	Version
07/04/2022	UK Health Security Agency	1.0

# **Background**

Infections caused by Gram-negative bacteria have been recognised as an increasing cause of healthcare-associated infections worldwide. Of concern is the spread of multi-drug resistant Gram-negative bacteria, with increased resistance to carbapenems being seen globally. Carbapenems are a family of antibiotics that are used to treat serious infections and are often viewed as an antibiotic of last resort for multi-drug resistant bacterial infections. Therefore, the spread of carbapenem-resistant organisms (CROs) will complicate the management and treatment of infections in vulnerable patients, including those in intensive care.

There are several resistance mechanisms that have been adopted by CROs, but much attention has been paid to the production of carbapenemase by Gram-negative Enterobacterales (previously Enterobacteriaceae). Enterobacterales are a large family of bacteria that are common causes of infections (including *Escherichia coli* and *Klebsiella* spp). Carbapenemase is an enzyme acquired by these organisms that destroys carbapenems. In the past ten years, we have seen clusters and outbreaks associated with CROs and carbapenemase-producing Enterobacterales (CPE) in hospital settings in England, particularly in London and Manchester. However, globally, some countries are seeing near endemic-levels of CRO/CPE being reported, particularly in the European Mediterranean, Balkan states and Indian sub-continent.

While the number of CPE infections is still relatively low in most of England, they are increasing. A retrospective microbiology review at a London hospital with low CPE prevalence found no carbapenem resistant *K. pneumoniae* reported in 2011, but found 1.3% of *K. pneumoniae* isolates were carbapenem resistant two years later. This represents a small but significant background rate of resistance. However, the epidemiology in England of CROs in general, and CPEs specifically, remains relatively unknown. We do know that there is significant variation in carriage and infection rates globally, but awareness of local prevalence and incidence is crucial to prevent spread, manage infections and identify appropriate treatment options.

In 2013, Public Health England (PHE) published a toolkit for acute trusts for detecting and managing CPE in the hospital environment. Considerable effort has been made to limit the propagation of these organisms, but further work must be done to reduce their impact. It is believed that carbapenem resistant infections are mostly healthcare acquired, but infections caused by many Enterobacterales are also found in the wider community. Therefore, there is a risk of colonisation or infection outside the hospital setting.

Currently, laboratory reports of carbapenemase-producing Gram-negative bacteria are notifiable. However, CRO/CPEs are not monitored as part of the mandatory healthcare associated infections surveillance system; though blood-stream infections caused by some specific Gram-negative organisms are included. It is proposed that CPEs specifically are monitored as part of the mandatory system, with an initial focus on the most vulnerable patient groups – namely, those patients on intensive care units. However, an understanding of the epidemiology of CPEs in England is necessary to help establish a baseline. As part of this, a national point prevalence survey of CPEs in intensive care units in England is planned for Spring 2022.

Point prevalence surveys (PPS) can be conducted to identify priority areas for surveillance and guide implementation of interventions to reduce infections. Performing a CPE PPS in intensive care units will provide us with an understanding of the current CPE situation in this patient group. Furthermore, this data can be used to identify patients who may require more focused interventions to prevent CPE infections and inform the development of infection prevention strategies.

The case for conducting a CPE PPS in ICUs has been presented to the Infection in Critical Care Quality Improvement (ICCQIP) board members and has support from ICCQIP's Chair.

#### **Methods**

# Aim and objectives

#### Aim

To generate an estimate of the prevalence of carbapenemase-producing *Enterobacterales* infections and colonisations among patients in intensive care units in England.

#### **Objectives**

- To describe patients, invasive procedures, infections, and antimicrobials prescribed.
- To estimate the prevalence of clinical isolates from ICU patients that are positive for carbapenemase-producing Enterobacterales.
- To estimate the prevalence of rectal screening isolates from ICU patients that are positive for carbapenemase-producing *Enterobacterales*.
- To understand patient characteristics, procedures, and antimicrobial use which are associated with CPE colonisation or infection
- To understand inequalities in the prevalence of CPE colonisation and infection.
- To raise awareness of the growing concern of CPE in ICU patients.

#### Study population

Patients of any age in critical care in England, in ICUs which provide levels 2 and 3 care for adults, level 3 care for paediatrics, and both high dependency units (HDUs) and critical care for neonates.

The selection of intensive care units as the focus for this survey is due to the unique characteristics of the patients admitted to these wards. These patients are highly vulnerable to infection. Patients in intensive care also often receive multiple courses of antibiotics, which has been identified as a risk factor for the acquisition of a CRO. The patient mix on these wards also means they often represent both surgical and medical specialities, which may give us wider insight into the true burden of both infection and colonisation with CPE.

#### **Trusts**

All NHS trusts which provide critical care in England are eligible for inclusion.

#### Wards

The wards of interest for this survey are specifically those that provide critical care. The survey will look at adult, paediatric, and neonatal wards. The care level indicated is age group-specific, based on the NHS England Critical Care Beds data for which the sample size has been calculated (levels 2 and 3 critical care for adults, level 3 only for paediatrics, and high dependency or critical care for neonates).

#### **Patients**

All patients admitted to the ward before or at 8am and not discharged from the ward at the time of the survey will have the chance to be recruited to the study. This means that patients transferred in/out of the intensive care unit after 8am from/to another ward should not be included in study recruitment.

# Study design

A prospective, cluster randomised cross-sectional survey approach will be used to provide estimates of prevalence of CPE for clinically indicated samples and rectal screening (stool sample or rectal swab) isolates from the randomly selected acute trusts.

Samples taken for routine clinical management purposes from the selected patients (e.g. blood, urine, wound) will be included, as will rectal screening (stool sample or rectal swab) taken to determine if the patient is colonised with a CPE.

The selected patients receiving in-patient treatment in the participating trusts' units will be included in the survey on the survey date. A single survey day will be used for each trust to minimise the workload for the clinical teams and to optimise sample collection.

Intensive care ward staff will implement the survey by randomly selecting patients and providing relevant data for the survey. To ease the workload, an online survey tool will be used for data collection purposes. ICU staff will be advised on methods of randomly selecting patients within the ward; the method by which patients are selected will be dictated by the number of critical care beds.

# Sampling procedure

Sampling will be carried out in the following stages:

- Sample size calculation for adults, paediatrics, and neonates based on total critical care populations for England (adults: levels 2 and 3, paediatrics: level 3 only, neonates: HDUs and neonatal critical care units)
- Weighting of sample size by NHS England (NHSE) region
- Calculation of number of trusts required per region, for adults, paediatrics, and neonates
- Cluster sampling:
  - Random selection of trusts in each region, using the list of NHS trusts with critical care beds as the sampling frame
  - Random selection of patients per trust (dictated by number of critical care beds)

# Sample size

For this study, three separate sample sizes will be calculated – for adult, paediatric, and neonatal ICUs. There are differences between the types and size of unit, and there are fewer paediatric intensive care beds than adult or neonatal. Stratified sampling strategy will help ensure we are able estimate the prevalence across population groups.

No studies have been carried out in English ICUs specifically to determine the prevalence of CPE. However, based on prevalence studies that have been carried out in hospital settings, hospital prevalence in England appears to lie between 0-11%. However, the upper range of that estimate was found at a hospital with a known outbreak, and therefore determined to not be representative. If we remove that upper estimate from consideration, the prevalence identified in trusts was up to 3-4%; this is still considered to be an overestimate nationally.

Population sizes were estimated using the NHS Statistics monthly critical care SitRep for September 2019. We used this time period as we aim to conduct the survey in September 2021. Data from March 2020 has not been published due to the COVID-19 response; however, as there would have been changes specific to September 2020 and the COVID-19 response, September 2019 data would have been used anyway. Some NHS trusts have merged since September 2019; the population and occupancies for those trusts have been aggregated in the tables below.

	Population (beds), n						
	Total trusts	Total beds	Min	Median	Max		
Adult	135	4090	2	18	192		
Paediatric	19	312	3	14	36		
Neonatal	107	1441	1	8	58		

	Occupancy, n						
	Total trusts	Total occupancy	Min	Median	Мах		
Adult	135	3305	1	14	142		
Paediatric	19	232	0	11	28		
Neonatal	107	1007	0	5	47		

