#### **Assumptions**

- Prevalence is assumed to be below 3%, and likely closer to 0.5-1%
- A confidence of 95% will be used for all groups.
- The intra-cluster correlation is not known but is assumed to be relatively small. A
  design effect of 2 will be used to account for the cluster design.
- The sample size has been increased by 10% in all patient groups to allow for noncompletion of the survey.

Sample sizes for a range of prevalences and absolute precisions have been calculated for each age group. The prevalence and precision detectable are limited in some cases, especially in paediatrics, by the number of ICUs (e.g. the sample size required to detect 1% prevalence with absolute precision of 1% in the paediatric population is 379, greater than the number of ICU beds).

Option	Assumed prevalence	Absolute precision	Total number of patients required
Adult			
1	1%	+/- 2%	205
2	0.5%	+/- 1%	403
3	1%	+/- 1%	767
Paediatric	;		
1	0.5%	+/- 3%	44
2	0.5%	+/- 2%	93
3	1%	+/- 2%	162
Neonatal			
1	1%	+/- 2%	197
2	0.5%	+/- 1%	372
3	1%	+/- 1%	664

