#### Sample size per region

In order to allow participation amongst ICUs of all sizes, we have estimated the average number of patients each unit will be able to collect data on in the one-day survey period. It is assumed that each ICU will be able to collect data on a maximum of 20 patients.

Using the occupancy data by region for September 2019, and capping at 20 patients per unit, the mean occupancies of adult, paediatric, and neonatal are calculated:

Mean occupancy if capped at 20				
NHSE region	Adults	Paediatrics	Neonates	
East of England	13	8	6	
London	15	12	11	
Midlands	13	9	9	
North East and Yorkshire	13	11	7	
North West	13	15	5	
South East	15	11	10	
South West	13	17	6	

For each prevalence/precision option, the number of ICUs needed is:

NHSE region	Adults	5		Paedia	atrics		Neona	ites	
Option	1	2	3	1	2	3	1	2	3
Prevalence	1%	0.5%	1%	0.5%	0.5%	1%	1%	0.5%	1%
Precision	2%	1%	1%	3%	2%	2%	2%	1%	1%
East of England	2	4	7	1	2	3	4	8	13
London	3	5	9	1	2	3	3	6	10
Midlands	4	6	12	1	2	4	5	9	15
North East and Yorkshire	3	5	10	1	2	3	5	9	15
North West	2	4	8	1	1	2	5	10	17
South East	3	5	9	1	2	3	4	6	11
South West	2	4	7	1	1	1	4	6	11
Total	19	33	62	7	12	19	30	54	92

Choosing the prevalence/precision option for each age group is a balance between what is clinically useful and what is feasible. For each age group, the larger number of trusts from the range of sample size calculations will be invited to participate: **62 trusts for adults, 19 for paediatrics, and 92 for neonates.** 

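### The sample sizes count ICU beds, not patients present, as the finite population, so the required sizes are modestly overstated (8–9% in paediatrics and neonates, 2% in adults)

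*Protocol*

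**What the plan says.** The Sample size section states that "Population sizes were estimated using the NHS Statistics monthly critical care SitRep for September 2019". It then gives two tables from that source. The one labelled as population counts beds: 4090 adult, 312 paediatric and 1441 neonatal. The other counts occupancy: 3305, 232 and 1007. The Wards section describes the care levels as "based on the NHS England Critical Care Beds data for which the sample size has been calculated".

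The Assumptions section sets the remaining inputs: "A confidence of 95% will be used for all groups", a "design effect of 2 will be used to account for the cluster design", and a 10% increase for non-completion. It reports that "Sample sizes for a range of prevalences and absolute precisions have been calculated for each age group". The table gives adult 205/403/767, paediatric 44/93/162 and neonatal 197/372/664 for options 1/2/3. As an example of a target out of reach, it gives the paediatric size for 1% prevalence with ±1% precision as "379, greater than the number of ICU beds". No finite-population correction is mentioned.

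The section Sample size per region turns the sizes into trusts by "Using the occupancy data by region for September 2019, and capping at 20 patients per unit". It invites the option 3 numbers: 62 adult, 19 paediatric and 92 neonatal trusts. The sections Patients and Sampling patients make the surveyed units patients who are on the ward on the survey day.

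**The concern.** A finite-population correction needs the number of units in the population whose prevalence is estimated. Here those units are patients present, and an empty bed has no CPE status. Beds exceed occupancy by 24% in adults (4090/3305), 34% in paediatrics (312/232) and 43% in neonates (1441/1007). If beds were used, the correction is too weak and the required sizes too large. The calculation would also change population midway, from beds for the size to occupied beds for the yield per trust.

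At stake are the column of patients required, the figure used to show that ±1% is unattainable in paediatrics, and the number of trusts asked to take part. The protocol itself describes the choice of option as a balance between clinical usefulness and feasibility, so the sizes entering that balance should be right.

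**Working it through.** **Inputs.** z = 1.96 (95% confidence), design effect 2, and a factor of 1.10 for non-completion, all from Assumptions. Prevalence p and precision d are taken from each row of that table. N is either beds or occupancy, from the tables in Sample size.

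**A correction was used.** At p = 1% and d = 2% the table gives 205, 162 and 197 for the three age groups. Every input except N is common to them, so N must enter the formula.

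**Formula.** n = 2·N·p(1−p) / [(d²/z²)(N−1) + p(1−p)], rounded up, multiplied by 1.10 and rounded up again.

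**Reproducing the plan.** Adult option 3 with N = 4090: 2 × 4090 × 0.0099 / [(0.0001/3.8416) × 4089 + 0.0099] = 696.1, then 697, then 697 × 1.10 = 766.7, then 767 as printed. The other rows follow in the same way:

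| Group, p, d | Stated | N = beds | N = occupancy |
|---|---|---|---|
| Adult 1% ±2% | 205 | 205 | 204 |
| Adult 0.5% ±1% | 403 | 403 | 399 |
| Adult 1% ±1% (chosen) | 767 | 767 | 752 |
| Paediatric 0.5% ±3% | 44 | 44 | 44 |
| Paediatric 0.5% ±2% | 93 | 93 | 88 |
| Paediatric 1% ±2% (chosen) | 162 | 162 | 150 |
| Paediatric 1% ±1% (example) | 379 | 379 | 318 |
| Neonatal 1% ±2% | 197 | 197 | 192 |
| Neonatal 0.5% ±1% | 372 | 372 | 355 |
| Neonatal 1% ±1% (chosen) | 664 | 664 | 609 |

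With beds, all ten figures match exactly. With occupancy, only the paediatric 44 does. With no correction, the 1% ±1% size would be about 837 in every group (2 × 0.0099 × 3.8416/0.0001 = 760.6, × 1.10 = 836.7), which also does not match.

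**Size of the excess.** 767/752 = 1.020, 162/150 = 1.080 and 664/609 = 1.090.

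**Trusts.** Trusts per region = size × regional population share / capped mean occupancy, rounded up, using the printed regional populations and means.
- Stated sizes: 61 adult (62 printed), 19 paediatric, and 92 neonatal with exact shares or 93 with the two-decimal shares (92 printed). The printed means are rounded, and some regional cells differ by one.
- Occupancy-based sizes: 57 adult with exact shares or 58 with two-decimal shares, 18 paediatric and 85 neonatal.

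**Precision at the stated sizes.** Before the 10% allowance the stated sizes are 697, 147 and 603. With n/2 as the effective size and N = occupancy, half-width = z·√[p(1−p)/(n/2) × (N − n/2)/(N−1)] at p = 1%:
- Adult (N = 3305): 0.99%, target 1%.
- Paediatric (N = 232): 1.88%, target 2%.
- Neonatal (N = 1007): 0.94%, target 1%.

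**The case against.** The best defence is that beds are a deliberate, disclosed ceiling. The table is openly labelled as a bed count, and the occupancy figures are from September 2019 while the survey moved to April 2022, with a separate survey day for each trust. The number of patients present is therefore uncertain, and capacity bounds it. Where a large unit subsamples, the suggested methods draw bed numbers. Using beds for N and occupancy for yield can only raise the number of trusts invited.

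Part of this stands. The choice errs on the safe side, and the arithmetic is correct for the input used. But the protocol nowhere presents beds as an allowance for full occupancy; its only stated margin is the separate 10%. Drawing bed numbers is a way to reach patients and does not bring empty beds into the population being estimated. The occupancy figures, although dated, are the ones the protocol itself relies on to convert sizes into trusts.

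One could also argue that the target is a wider population over time, so that no correction applies and the printed sizes are too small (about 837 for 1% ±1%). The protocol does not take that view: its sizes embed a correction.

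A reader might infer from the point that the survey's precision is compromised, or that the paediatric ±1% example is wrong in its conclusion. Neither follows. Every precision target is met at the stated sizes, and 318 still exceeds the 232 patients.

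**Conclusion.** The point holds as a modest, conservative error in the population used for the correction. It is material in neonates (664 against 609, 9.0%) and paediatrics (162 against 150, 8.0%) and small in adults (767 against 752, 2.0%). In trusts, the excess over what the stated targets need is about seven neonatal (92 against 85), one paediatric (19 against 18) and four or five adult (62 against 57–58).

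These trust differences are approximate. The adult figure is the softest, because the printed inputs give 61 rather than 62. The 19 paediatric trusts are the whole sampling frame, so at most one could be spared there.

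The conclusion rests on three assumptions: that a finite-population correction was applied, which is inferred from exact reproduction because the protocol does not say so; that the target is the patients present on the survey day; and that the September 2019 occupancy is the working estimate of their number. The position of the design effect in the formula was left as the plan has it.

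**What to change.** - Recompute the table of sizes in Assumptions with N = 3305, 232 and 1007.
- Restate the paediatric example as 318 and compare it with 232 patients rather than with the number of beds.
- State that a finite-population correction is used and which population it takes.
- In Sample size per region, either update the trust numbers (about 57–58, 18 and 85, from the sponsor's unrounded regional means) or keep 62, 19 and 92 as an explicit margin and state the precision they deliver, about ±0.99%, ±1.88% and ±0.94% at the stated sizes.

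The cost is recalculating one or two tables and rewording a few sentences. No extra patients or data are needed. Keeping the invited trusts is the simpler course if invitations have already gone out, since the Timeline places contact with hospitals in February 2022 and this version is dated April 2022.

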#### **Assumptions**

- Prevalence is assumed to be below 3%, and likely closer to 0.5-1%
- A confidence of 95% will be used for all groups.
- The intra-cluster correlation is not known but is assumed to be relatively small. A
  design effect of 2 will be used to account for the cluster design.
- The sample size has been increased by 10% in all patient groups to allow for noncompletion of the survey.

Sample sizes for a range of prevalences and absolute precisions have been calculated for each age group. The prevalence and precision detectable are limited in some cases, especially in paediatrics, by the number of ICUs (e.g. the sample size required to detect 1% prevalence with absolute precision of 1% in the paediatric population is 379, greater than the number of ICU beds).

Option	Assumed prevalence	Absolute precision	Total number of patients required
Adult			
1	1%	+/- 2%	205
2	0.5%	+/- 1%	403
3	1%	+/- 1%	767
Paediatric	;		
1	0.5%	+/- 3%	44
2	0.5%	+/- 2%	93
3	1%	+/- 2%	162
Neonatal			
1	1%	+/- 2%	197
2	0.5%	+/- 1%	372
3	1%	+/- 1%	664

#### Weighting of sample size by NHSE region

All age mid-year population estimates from 2019 are used to stratify the population in England.

NHSE region	Population (all ages)	Proportion of total
East of England	6,600,056	0.12
London	8,961,989	0.16
Midlands	10,557,979	0.19
North East and Yorkshire	8,618,242	0.15
North West	7,013,321	0.12
South East	8,910,678	0.16
South West	5,624,696	0.10
Total	56,286,961	-

#### Sample size per region

In order to allow participation amongst ICUs of all sizes, we have estimated the average number of patients each unit will be able to collect data on in the one-day survey period. It is assumed that each ICU will be able to collect data on a maximum of 20 patients.

Using the occupancy data by region for September 2019, and capping at 20 patients per unit, the mean occupancies of adult, paediatric, and neonatal are calculated:

Mean occupancy if capped at 20				
NHSE region	Adults	Paediatrics	Neonates	
East of England	13	8	6	
London	15	12	11	
Midlands	13	9	9	
North East and Yorkshire	13	11	7	
North West	13	15	5	
South East	15	11	10	
South West	13	17	6	

For each prevalence/precision option, the number of ICUs needed is:

NHSE region	Adults	5		Paedia	atrics		Neona	ites	
Option	1	2	3	1	2	3	1	2	3
Prevalence	1%	0.5%	1%	0.5%	0.5%	1%	1%	0.5%	1%
Precision	2%	1%	1%	3%	2%	2%	2%	1%	1%
East of England	2	4	7	1	2	3	4	8	13
London	3	5	9	1	2	3	3	6	10
Midlands	4	6	12	1	2	4	5	9	15
North East and Yorkshire	3	5	10	1	2	3	5	9	15
North West	2	4	8	1	1	2	5	10	17
South East	3	5	9	1	2	3	4	6	11
South West	2	4	7	1	1	1	4	6	11
Total	19	33	62	7	12	19	30	54	92

Choosing the prevalence/precision option for each age group is a balance between what is clinically useful and what is feasible. For each age group, the larger number of trusts from the range of sample size calculations will be invited to participate: **62 trusts for adults, 19 for paediatrics, and 92 for neonates.** 

